6.1.1 Adverse Event (AE)

An adverse event (AE) is any untoward medical occurrence in a subject to whom a medicinal product has been administered, including occurrences which are not necessarily caused by or related to that product.

6.1.2 Adverse Reaction (AR)

An adverse reaction (AR) is any untoward and unintended occurrence in a subject to whom a medicinal product has been administered, which is thought to be caused by or related to that product.

Version 6: 16th July 2021 Page 48 of 87

6.1.3 Serious Adverse Event (SAE)

A serious adverse event (SAE) is defined as any of the following, whether or not considered related to the trial treatment.

- · Results in death
- Life-threatening (i.e. at the time of the event)*
- Requires inpatient hospitalisation or prolongation of existing hospitalisation**
- · Results in persistent or significant disability or incapacity
- Is a congenital anomaly/birth defect
- Is considered medically significant by the Investigator***

*Life threatening means that the patient was at immediate risk of death from the event as it occurred. It does not include an event that, had it occurred in a more serious form, might have caused death.

**Requires in-patient hospitalisation should be defined as a hospital admission required for treatment of an adverse event.

***Considered medically significant by the Investigator, are events that may not result in death, are not life threatening, or do not require hospitalisation, but may be considered a serious adverse experience when, based upon appropriate medical judgement, the event may jeopardise the patient and may require medical or surgical intervention to prevent one of the outcomes listed above.

6.1.4 Serious Adverse Reaction (SAR)

A serious adverse reaction (SAR) is a SAE that may be related to trial treatment. The assessment of "relatedness" is primarily the responsibility of the PI at site or agreed designee. SAEs will be considered related if the SAE is documented as possibly, probably or definitely related to protocol treatment. The assessment of relatedness is made using the following:

Relationship	Description
Unrelated	There is no evidence of any causal relationship.
Possible	There is some evidence to suggest a causal relationship (e, g. the event occurs within a reasonable time after administration of the trial medication). However the influence of other factors may have contributed to the event (e.g. the patient's clinical condition, other concomitant treatments).
Probable	There is evidence to suggest a causal relationship and the influence of other factors in unlikely.

Version 6: 16th July 2021 Page 49 of 87

Definitely	There is clear evidence to suggest a causal relationshi	
	and other possible contributing factors can be ruled out.	

6.1.5 Suspected Unexpected Serious Adverse Reaction (SUSAR)

A Suspected Unexpected Serious Adverse Relation (SUSAR) is any suspected SAR that is unexpected. Unexpected is any reaction that is not a known reaction listed in the section of the current regulatory approved SmPCs, which are acting as the reference safety information (RSI) for the trial treatments. Please note the version of the RSI that has regulatory approval may not be the most up-to-date version of the SmPC that has been provided to Investigators for advice on the clinical management of their trial patients.

6.2 Detecting, Recording and Reporting of Adverse Events

6.2.1 Detection of Adverse Events

Participants will be asked at each trial visit about the occurrence of AEs since the last visit.

AEs will be recorded, notified, assessed, reported, analysed and managed in accordance with the Medicines for Human Use (Clinical Trials) Regulations 2004 (as amended) and the trial protocol.

AEs must be recorded as they are reported, whether spontaneously volunteered or in response to questioning about wellbeing at trial visits. The questioning about AEs will cover the current visit as well as the period of time between the previous and the current visit. All adverse events must be documented in the patient's medical records and in the CRF as required.

6.2.2 Recording of Adverse Events

Full details of AEs including the nature of the event, start and stop dates, severity, relationship to trial drug and outcome will be recorded in the patient's medical records. However, only AEs that are grade 2 or above require entry on the trial CRF. All AEs must be followed until they resolve or return to the baseline value, or if they do not resolve, for at least 30 days after discontinuation of trial medication or until they are confirmed as likely to never resolve. Perceived lack of efficacy is not an AE. An exacerbation of a pre-existing condition is an AE.

6.2.3 Assessment of Adverse Events

All AEs and toxicities must be graded according to the NCI-CTCAE Version 4. These criteria can be accessed via the National Cancer Institute Website.

AEs must be assessed for seriousness, causality and severity. This assessment is the responsibility of the PI (or designee).

Version 6: 16th July 2021 Page 50 of 87

Reporting of a Serious Adverse Event 6.3

SAEs must be reported by email or fax to the Pharmacovigilance Office, CRUK Glasgow CTU

immediately and under no circumstances should this exceed 24 hours following first awareness of the

event by the Investigator or site staff:

Pharmacovigilance Office, CRUK Glasgow CTU

[contact]

[contact] or [name]

Email: [contact]

For guidance on submitting and completing initial and follow up SAE report forms please refer to the

SAE Completion Guidelines, which will be provided by the Pharmacovigilance (PV) Office, CRUK

Glasgow CTU.

All initial SAE reports will have a SAE reference number generated for the event and will be

acknowledged by the Pharmacovigilance Office. If no acknowledgement is received within 48 hours

sites are required to contact the Pharmacovigilance Office to check the report has been successfully

submitted and received.

When the causality of a SAE is assessed by Investigators to be unrelated to the IMPs, Investigators

must include in the SAE report what the SAE is related to i.e. whether the SAE is assessed as being

related the disease under investigation, a concurrent illness or concomitant medication, or another

possible cause.

When no causality is provided by an Investigator the SAE will, for the purposes of regulatory reporting,

be treated as related to the IMP until a causality assessment is provided by the Investigator.

If a SAE is the result of a protocol related procedure this must be clearly explained in the SAE report.

The Chief Investigator (CI) will be notified by e-mail of all SAEs received. . SAEs must be reported locally

by the Investigator at each site in accordance with the local practice at their site (i.e. Datix or R&D

Office).

A follow-up report must be completed when the SAE resolves, is unlikely to change, or when additional

information becomes available. If the SAE is a potential SUSAR then follow up information must be

Version 6: 16th July 2021

Page 51 of 87

provided quickly and in the timeframe requested by the CRUK Glasgow CTU and CI. Information in addition

to what is recorded in the SAE report form may be required to submit a SUSAR report to the Regulatory Authority.

All follow-up information for SAEs that are not SUSARs, also requires to be reported promptly, and

follow up reports must be submitted until all SAEs listed on the initial SAE report resolve. A follow-up

report must be submitted if additional SAEs listed on the initial SAE report resolve, or it is confirmed

that they will never resolve. A follow-up report should also be submitted if additional SAEs occur or

new information becomes available about previously reported SAEs.

Any event that meets the criteria for a SAE (including events that the Investigator thinks are medically significant

but maybe do not require hospitalisation or are not fatal etc.) that occurs after 30 days post treatment is also

required to be reported if the Investigator thinks the SAE is related to protocol treatment and is medically

important. Such SAEs must be reported to the Pharmacovigilance office without undue delay and within 24 hours

of first knowledge of the event.

For any questions relating to SAE reporting, please contact the PV team, contact details are provided

below and at the front of the protocol and in the SAE Completion Guidelines.

Pharmacovigilance Office, CRUK Glasgow CTU

[contact]

[contact] or [name]

Email: [contact]

6.4 When SAEs are not required to be Reported

SAEs that occur after consent and randomisation but prior to any trial treatment do not require to be

reported.

In addition, the following events also do not require to be reported as SAEs:

SAEs that are unrelated to the trial treatment

Hospitalisation or death due to disease progression if trial treatment has ended

Hospitalisation for planned investigations

Hospitalisation for trial drug administration, palliative care, terminal care or elective surgery

Version 6: 16th July 2021

Page 52 of 87

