10.3 Management of protocol deviations and violations

Incident Reporting

Organisations must notify the Sponsor (via CRUK Glasgow CTU) of all deviations from the protocol or GCP immediately. The Sponsor requires a report on the incident(s) and a form will be provided prior to site initiation. If site staff are unsure whether a certain occurrence constitutes a deviation from the protocol or GCP, the CRUK Glasgow CTU trial team and Sponsor can be contacted immediately to discuss. The Sponsor will assess all incidents against the definition of a serious breach.

Serious Breach

In addition to the definition of a serious breach in GCP, systematic or persistent violation by a site with GCP and/or the protocol, including failure to report SAEs occurring on trial within the specified timeframe, may be deemed a serious breach. In cases where a potential or actual serious breach **Version 6: 16th July 2021**Page 63 of 87

has been identified, the Sponsor (via CRUK Glasgow CTU) will inform the MHRA within 7 calendar days of becoming aware of the breach.

Sites must have written procedures for notifying the Sponsor of serious breaches (MHRA Guidance on the Notification of Serious Breaches, 2009).

The Sponsor and CRUK Glasgow CTU will use an organisation's history of non-compliance to make decisions on further collaborations.

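### Protocol sections 6.3 and 6.4 give opposite instructions for serious adverse events judged unrelated that occur on treatment or within 30 days after it

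*Protocol*

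**What the plan says.** Section 6.1.3 sets the definition: "A serious adverse event (SAE) is defined as any of the following, whether or not considered related to the trial treatment". It says what counts as an SAE; it does not itself impose a reporting duty.

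The duty is in section 6.3: "SAEs must be reported by email or fax to the Pharmacovigilance Office, CRUK Glasgow CTU", at once and never later than 24 hours after first awareness. No relatedness condition is attached. The same section deals expressly with events judged to have no link to the trial drugs. For these, it says, the site "must include in the SAE report what the SAE is related to i.e. whether the SAE is assessed as being" due to the disease, another illness or medication, or some other cause. For events later than 30 days after treatment, 6.3 adds a narrower duty: they are "required to be reported if the Investigator thinks the SAE is related to protocol treatment and is medically" important.

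Section 6.4 lists what need not be reported as an SAE. One bullet reads "SAEs that are unrelated to the trial treatment", without a time limit. Another reads "Hospitalisation or death due to disease progression if trial treatment has ended".

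Section 10.3 says that systematic or persistent violation by a site, "including failure to report SAEs occurring on trial within the specified timeframe, may be deemed a serious breach".

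**The concern.** A site with an on-treatment SAE that it considers unrelated has two instructions. Section 6.3 tells it to send a report within 24 hours and to name the other cause. Section 6.4 tells it that no report is needed.

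The choice has consequences. Causality is assessed by the local principal investigator or a designee, and the trial is open-label. If 6.4 governs, that local judgement decides whether the Pharmacovigilance Office receives an SAE report at all. The central safeguards act only on what arrives: the Chief Investigator is notified of SAEs received (6.3) and decides whether SAEs are SUSARs (12.3). An event stopped locally gets no SAE reference number, follow-up report or second opinion on causality. If some sites follow 6.3 and others 6.4, SAE counts are not comparable between UK sites.

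**Working it through.** No arithmetic applies. The check is whether the provisions can all be followed for one event: an SAE on treatment, or within 30 days after it, that the investigator judges unrelated.

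| Provision | What it implies for that event |
|---|---|
| 6.1.3, definition | It is an SAE; relatedness is not a criterion |
| 6.3, general duty | Report within 24 hours |
| 6.3, content rule for unrelated SAEs | The report must name the other cause, so a report is expected |
| 6.3, events later than 30 days | Relatedness is a condition only for these, so not for this event |
| 6.4, unrelated-SAE bullet | No report needed |

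**Step 1: direct conflict.** The second and third rows require a report; the last dispenses with it. Both cannot be followed.

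**Step 2: can 6.4 be read as an exception to 6.3?** If every unrelated SAE is exempt at all times, three other provisions lose most of their purpose:

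- The 6.3 rule on the content of a report for an unrelated SAE would govern a report that is not required.
- The 6.3 relatedness condition after 30 days would single out late events for a condition that already applied to earlier ones.
- The 6.4 bullet on progression applies only once trial treatment has ended. Section 6.3 counts the disease under investigation among the causes of an unrelated SAE, so progression events would already be exempt during treatment, and the limit would do almost nothing.

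The exception reading therefore does not make the text coherent. The unrelated-SAE bullet also sits badly with its neighbour in 6.4.

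**Step 3: what is lost if 6.4 is followed?** The other routes by which such an event is recorded are:

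| Route | Source | Relatedness filter |
|---|---|---|
| Adverse events of grade 2 or above on the CRF | 6.2.2 | None |
| Hospital inpatient data on treatment and follow-up forms | 4.1.4 | None stated |
| Death from any cause as a DFS event | 4.3.1 | None |
| Survival status at each follow-up visit | 4.3.2 | None |

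The event therefore largely remains in the trial data, and the data monitoring committee reviews safety data and critical efficacy endpoints (10.6). What is lost is speed and central handling. Section 9.3 chases outstanding data quarterly and asks for return within 6 weeks. It contacts a site when 20% of its forms (at least 10) are more than 3 months overdue, or any form is more than 6 months overdue. The SAE limit is 24 hours.

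**Step 4: which analyses depend on SAE reports?** The primary analysis uses DFS (7.3.1). The safety comparison for the oxaliplatin question uses the worst CTCAE grade in the treatment period (7.3.3). Neither is built on SAE forms.

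**Step 5: reach.** Section 6 states that its definitions and reporting requirements apply to BALLAD UK only, and other countries make their own safety arrangements (section 3). On the recruitment chart for question 1 in section 7.2, the UK had 10 of 77 patients, or 10/77 = 13%.

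**The case against.** The strongest reply is that 6.3 states a general rule and 6.4, under a heading about when reports are not required, states the exceptions. A site relying on an express exemption could argue that no report was due. Section 10.3 helps it, since that section speaks of systematic or persistent violation and says only that this may be deemed a serious breach. The structural point is fair, but step 2 shows that it leaves three provisions with little purpose. The serious-breach text shows that a site is exposed to argument, not that following 6.4 is a breach.

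A second reply is that the causality filter is loose. Section 6.1.4 counts a possible relationship as related, and 6.3 treats an SAE without a causality assessment as related. Many on-treatment events would therefore be reported anyway. This stands and reduces the number affected. It does not help once an event has been called unrelated.

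A reader might go further and infer that serious events and treatment-period deaths could go unseen, or that the oxaliplatin safety comparison is filtered by opinion. The documents do not support either. Steps 3 and 4 show other recording routes with no relatedness filter, and a planned comparison based on graded toxicity. Nor can the effect be extended to the pooled GLOBAL BALLAD data, because section 6 covers UK sites only. The documents do not give the share of SAEs that would be called unrelated, so any percentage of missing reports would be a guess.

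**Conclusion.** The contradiction is real and wrong as written: 6.3 and 6.4 cannot both be followed for an unrelated SAE on treatment or within the next 30 days. It needs correcting because it concerns a mandatory safety instruction. The harm is limited to expedited reporting, Chief Investigator notification and SUSAR review, SAE follow-up and complete SAE counts at BALLAD UK sites that follow 6.4. Treatment-period deaths judged unrelated are included. The number of events cannot be derived from the protocol.

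The conclusion that reporting before the 30-day point is meant to be independent of cause is an inference from 6.3; no sentence says so outright. The conflict itself does not rest on that inference, because the content rule for unrelated SAEs is enough to establish it.

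**What to change.** Reconcile 6.3 and 6.4. The smallest edit consistent with 6.3 is to delete the unrelated-SAE bullet from 6.4, or to limit it to events more than 30 days after treatment. The other specific exemptions stay as they are. It would help if 6.3 also stated its reporting window directly, so that the window need not be inferred from the clause on late events. Sites should be told by memo which rule applies.

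If the sponsor does intend to exempt unrelated SAEs throughout, 6.3 must be rewritten to match (the content rule for unrelated events and the 30-day condition), the progression bullet in 6.4 reconsidered, and the exemption justified.

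The first route costs a short protocol amendment, the memo and a modest number of extra SAE forms at UK sites. No analysis or sample size changes.

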6.5 Reporting of a SUSAR

CRUK Glasgow CTU on behalf of the Sponsor is responsible for the expedited reporting of all SUSARs to the required regulatory authority, Research Ethics Committee (REC), Investigators at trial sites and the trial Sponsor.

- Fatal or life threatening SUSARs will be reported within 7 days of the CRUK Glasgow CTU receiving the first notification of the unexpected event. Any additional information will be reported within eight days of sending the initial report.
- All other SUSARs will be reported within 15 days of the CRUK Glasgow CTU receiving the first notification of the unexpected event.

6.6 Pregnancy

Pregnancy occurring in a participant in the trial or the partner of a trial participant, while not considered an AE or SAE requires to be monitored and followed-up.

The Investigator must collect pregnancy information for female trial subjects or the female partners of trial subjects. This includes subjects who become pregnant whilst receiving trial drugs or for 12 months post trial treatment.

Any pregnancy occurring in a female subject or female partner of a male subject, while participating in the trial, must be reported by the Investigator (or designee) to Pharmacovigilance using the Pregnancy Notification Form (PNF) within 24 hours of the Investigator first becoming aware of the pregnancy. Pharmacovigilance will track the pregnancy until confinement. Pharmacovigilance will also request an anticipated delivery date. However, the Investigator is required to update and submit the PNF immediately with the outcome of delivery or if there is a change in the subject's condition such as miscarriage or termination or if new relevant information becomes available concerning the child. The updated PNF must be emailed ([contact]) or faxed to the PV office ([name]) as soon as the new information becomes available. Any pregnancies which result in a congenital anomaly or birth defect will require to be reported by the Investigator as a SAE. The Pharmacovigilance department will assist with providing guidance on reporting pregnancy outcomes as SAEs. SAEs that are the result of a birth defect are likely to be reported as SUSARs. Additionally, any defects or health concerns with the infant that become known post-delivery, must also be reported by the Investigator by submitting an updated PNF. Development Safety Update Reports

6.7 Development Safety Update Reports

The Development Safety Update Reports (DSURs) will be prepared for the BALLAD trial rather than by trial drug. The reports will be written by the CI and CRUK Glasgow CTU on behalf of the Sponsor. DSURs will be submitted to the Regulatory Authority, REC, U.K. and trial Sponsor within 60 days of the anniversary of obtaining the UK Clinical Trial Authorisation by the CRUK Glasgow CTU.

Version 6: 16th July 2021 Page 53 of 87

6.8 Reference Safety Information

The contents of Section 4.8 Undesirable Effects in the reference SmPCs identified by the Sponsor for Capecitabine, 5-Fluorouracil, Folinic acid and Oxaliplatin will act as the Reference Safety Information (RSI) for the trial. The Sponsor is responsible for identifying and informing the CRUK Glasgow CTU of updates to the RSI. The SmPCs with current regulatory approval for the trial will be used to assess SAE reports to identify SUSARs. The CI, Pharmacovigilance and the Sponsor will decide if updates to RSI will be implemented or if the RSI is to remain unchanged. Any update to the RSI that includes the addition of new expected reactions, will not be implemented until regulatory approval has been received for the update and the new DSUR reporting period has started.

The Sponsor is responsible for identifying and informing the CRUK Glasgow CTU of updates to the reference SmPCs. Investigators will be supplied with SmPCs and updated SmPCs when the Sponsor and/or CI conclude the update will assist with the clinical management of trial patients.

When updated SmPCs are circulated to Investigators for the Clinical Management of their trial patients a *front sheet* document will also be provided. The front sheet will record what is to be referred to by Investigators for clinical management and why the updated SmPC is being circulated.

6.9 COVID-19 vaccination and Safety Reporting

Where a deployed COVID-19 vaccine is suspected to be involved in the onset of a reported event it should be recorded as a concomitant medication. A causal relationship between the vaccine and the event, including potential drug interactions should be assigned by the reporting investigator.

If a reported event is suspected to be due to a deployed COVID-19 vaccine alone reporting investigators should ensure that standard Yellow Card reporting procedures are followed.

7 STATISTICS AND DATA ANALYSIS

7.1 Trial Design

The rare nature of the tumour means that the GLOBAL BALLAD collaboration is not designed to provide the level of evidence usually required from a stand-alone clinical trial. Instead the approach taken combines the frequentist approach of a randomised phase II screening trial with a Bayesian approach to combining and summarising evidence.

The sample size to answer each of the two trial questions (Adjuvant question/Oxaliplatin question) is derived from a conventional phase II screening design with 90% (or 80% depending on accrual) power to detect a difference in disease-free survival between the trial arms at the 20% 1-sided level of statistical significance. If the result from this trial is statistically significant at the 1-sided 20% level, the following will be done:

Version 6: 16th July 2021 Page 54 of 87

(i) The estimate of the hazard ratio for DFS obtained from the trial will be combined with prior beliefs obtained from clinicians. The posterior distribution derived from the trial data combined with the clinician prior will be used as the summary of the final trial results in terms of DFS. The clinician prior will be elicited from a group of experts using a graphical method with clear instructions and a standardised script, combined with examples and training exercises.

(ii) The observed hazard ratio for OS obtained from the trial will be combined with predicted OS for those patients who are still alive at the end of the trial. This prediction will be based on observed DFS and other patient characteristics/interim observations. This observed/predicted OS estimate will then be combined with prior beliefs obtained from clinicians, in the same way as for DFS, to obtain a posterior distribution for OS

